9.1.1 Objective

- i) To compare the acceptability, uptake and implementation of HWS in LEOs versus SMEs. (WP3)
- ii) To evaluate the effectiveness, costs and value for money of the HWS intervention from the perspectives of employees, employers, the healthcare system and wider economy (WP3)

9.1.2 METHOD and DATA

Quantitative data to be collected (Participant-level data)

Participant questionnaires

In addition to the collection of screening and consent data, immediately following consent, all participants (both in the intervention and control SMEs) will be invited to complete a baseline study questionnaire (database form 3) using the same REDCap link enquiring into work engagement (primary outcome) and secondary outcomes (as per WP1 above).

Our data collection methodology and design will consider survey fatigue and time constraints on SME employees, aiming for completion within 15 minutes. Data collection tools will capture information on work engagement (primary study outcome) and various secondary outcomes (encompassing health and occupational measures, and resource use-/cost-related measures) along with other co-variates (e.g. demographic characteristics and organisational factors). These could include:

Demographics

- Age
- Sex
- Job role

Health outcomes

- Primary outcome: Work Engagement (UWES)
- Secondary outcomes:
 - Health-related quality of life (e.g. EQ-5D-5L)
 - Mental wellbeing (WHO-5)
 - Health behaviours (7-Day Physical Activity Recall Question)
 - Safety behaviours (Work Safety Scale (WSS))

Occupational outcomes

- “Employees’ perspective” (single item job satisfaction)
- “Employers’ perspective” (productivity (WPAI scale)) Resource use measures
- SMEs and LEOs: Financial investment and time investment (of management and paid time of employees) in HWS scheme and specific resources used in the delivery of the intervention
- Employees: Financial investment (purchasing additional materials to support their involvement in the intervention and changes in their lives outside of the workplace, e.g. signing up to the gym) and time investment outside of paid work time.
- Wider economy: DOH (e.g. GP appointments, hospital visit) and DWP (e.g. social security expenditures)

In the middle of the 12-month intervention period (6-months), participants will be invited to complete a short survey, which will ask about the primary outcome (work engagement) and, if they are in the intervention arm, will also ask if they are aware of all available HWS offers, if they have engaged with any of the offers, and their interim thoughts on these offers. At the end of the 12-month intervention period, and at 18 months, all study participants will complete a follow-up questionnaire (database form 4 & form 5) like that at baseline, with

further questions about engagement with specific components of the HWS for those in the intervention group (supplementary Fig 2).

Implementation of Organisational Engagement Activity Log

Throughout the HWS intervention implementation period, intervention fidelity and participants' engagement related activities will be monitored and documented using an online engagement activity log. The activity log will serve three purposes:

i) To act as a central repository for all SHINE activity within each SME. Recognising that each SME is likely to have different ways of working and communication channels, and each H&W Champion is likely to have multiple demands on their time, the activity log will allow information to be gathered in a consistent way across organisations, and act as a live 'to do' list and activity log for both the H&W Champion and their Advisor to keep track of progress.

ii) It is envisaged that the H&W Champions and the Advisor will use the activity log as a platform for discussion during monthly meetings, optimising the value of the study through the early identification of implementation issues and facilitating identification of practical actions to be taken to overcome challenges.

iii) It will provide an opportunity to monitor the HWS intervention implementation, intervention fidelity and participants' engagement in related activities, and will be analysed in the process evaluation and triangulated with qualitative and quantitative data gathering (WP4).

NOTE: To ensure participant confidentiality, NO personal identifiable information will be recorded in this activity log.

Data handling and recording keeping

SURVEY DATA

During conduct of this study, the research team will not disclose or make use of any information other than for its intended purpose. All survey data will be collected and initially stored using sponsor approved REDCap (electronic software database) and access to the source data within the software portal will be password protected, and only accessible by authorised persons i.e. central study team only. A back-up paper-based survey will be available upon request and on their return to the study team using a business reply envelope, data will be entered by the research team into the REDCap database and paper records will be securely stored by the research team in a locked cupboard in the Occupational Health, Safety and Wellbeing Service at Guy's and St Thomas NHS Foundation Trust) prior to long-term storage.

Personal identifiable data will be stored on the REDCap software for the duration of the study and personal identifiable data will only be accessible for members of the study team based at Guy's and St Thomas NHS Foundation Trust. However, all downloaded data files from REDCap will have personal identifiable data removed at the point of data extraction and at this point the data file will then become fully pseudonymised and kept in a secure, password file, and only accessible by the study team responsible for conducting the study. Additionally, the separate personal data extracted at the time of download will be removed

from the main data file, along with information on the specific reasons why they provided their contact information (i.e. to be entered into the prize draw, to hear about the study results). Included in this contact information data file will be each participant's unique study ID, and this will be used to link participants' contact information back to their response. This will mean that the survey will be pseudonymized for the duration of data analysis and storage. If it is necessary to email data files among research team members, this will be done by sending securely via email in encrypted and password protected data files. Passwords will be sent to the recipient in a separate email.

Paper-based questionnaires returned to the central study team will be manually entered into the database (REDCap software) by the study team member. To securely return completed questionnaires, participants who choose to complete a paper survey will be provided with a pre-paid business reply envelope marked 'Confidential'. Upon receipt by the research team, paper-questionnaires will be processed in a timely manner.

Participants will be informed in the PIS that they can withdraw from the study at any point during the study period (up to 31 March 2027) without giving a reason. For participants completing the survey online, they can close the browser before submitting their answers at any point, if they wish to discontinue. Those completing a paper survey will be able to destroy the survey themselves or submit the incomplete survey to the research team. Incomplete surveys which are returned to the research team, either via secured post for paper surveys or submitted on REDCap for online surveys, will be included in the analysis.

As the data collected by the survey will be pseudonymized, we can allow participants to withdraw their data after they have submitted the survey, should they desire. Participants will be made aware that they should contact the research team if they would like to withdraw their data. If this occurs, we will use their contact information to identify responses. If an individual did not provide their contact information but would like to withdraw their data, we will use their date of birth and demographic information to identify their record. Participants who did not provide sufficient data required to undoubtedly identify their response will be told that it is not possible to withdraw their data. Participants will be informed in the PIS that they will not be able to amend their data once their survey has been submitted.

ENGAGEMENT ACTIVITY LOG

Engagement activity logs will take the form of an excel spreadsheet, word document or paper version, depending on H&W champion preference. To optimise buy-in to maintaining the activity log, the activity log will be co-developed with the H&W champions during training led by the H&W advisor. The log's format will ensure it meets study aims and engages champions optimally. Held by the H&W champion, the activity log will likely include key metrics regarding:

- i) Activities offered to SME employees, including eligibility and uptake
- ii) Communications shared within the SME, including key content components, channel and date
- iii) Actions devised with the H&W advisor to help track actions to promote H&W offers within the organisation
- iv) Questions or concerns raised by employees, including a place to log questions to discuss at monthly meetings with the advisor or in peer-conversations.

- v) Reflections, including an open section for champions to reflect on what works, what doesn't, obstacles and opportunities.

The H&W advisor, supported by the Affinity research team members, will work with the H&W champions to identify the most acceptable format of hosting and managing the activity log. Ideally, we will work with electronic versions of the activity log, stored on a shared MS Teams site to which the H&W champion and the H&W advisor both have access. However, recognising that not all SME organisations will use Teams/ MS and some may have limited access to computers/ phones during working hours, hard copy activity logs may also need to be made available. In this eventuality, as hard copies can be lost, hard copies will be gathered quarterly with learnings captured during meetings to ensure there is a backup of information. Once the format and process for maintaining the activity log has been agreed, detailed instructions on monitoring and documenting will be shared to ensure consistency; and the importance of accurate maintenance of the activity log will be raised during monthly meetings between the champions and advisor. Where necessary, adaptations will be made to enhance usability to optimise the information gathered.

After site closure, each participating site will archive their research data in accordance with instructions from the Sponsor for a period of 2 years. The process of destroying documents will be in accordance with the standard procedures of the Sponsor.

A full description of the data flow is provided in the study's Data Protection Impact Assessment document. The chief investigator will be acting as data custodian during the conduct of the study.

Data sharing

Pseudonymised questionnaire data collected in the survey will be transferred out from Guy's and St Thomas NHS Foundation Trust (as sponsor) to our research partners based at Affinity Health at Work and at the University of Leeds for the analyses. This will not include any of the participants' identifiable data. The pseudonymised data files will be encrypted and password protected and shared securely via email. Passwords will be sent to the recipients in a separate email.

At the end of the study, data collected in the engagement activity log will be transferred from Affinity Health at Work to Guy's and St Thomas NHS Foundation Trust (as sponsor).

All data transferred to Guy's and St Thomas NHS Foundation Trust will be archived as per the study's long-term archiving requirements.

9.1.3 Outputs:

- i) Study implementation and collected data at three time points (WP2)
- ii) Study engagement activity log (WP2)
- iii) List of study implementation challenges and changes made (WP2)
- iv) Resources used by SMEs and LEOs in intervention delivery (WP2)
- v) Effectiveness analysis results (WP3)
- vi) List of factors that moderate impact of intervention (WP3)
- vii) Economic evaluation including Social Return on Investment (SROI)(WP3)

9.2 Work Package 4: Process evaluation and feedback (Lead: JY)

9.2.1 Objectives:

- i) To explore perceived obstacles and facilitators by champions to deliver the study intervention to employees in their organisational settings
- ii) To explore champions' perceived level of upskilling, and sustainability of skill proficiency
- iii) To gather feedback from stakeholders regarding the intervention
- iv) To explore transferability of a supply chain approach with cross-sector OH and wellbeing leads

9.2.2 Participant inclusion criteria

We'll conduct focus groups with champions in all intervention SMEs to explore their training experience, resulting acquisition and maintenance of skills over the study period, and confidence in delivering the study intervention. Questions will further examine sustainability of skills acquired and level of supplementary training required to achieve established competency goals and maintain skill proficiency.

We will also conduct semi-structured interviews with key stakeholders in SMEs and LEOs to explore engagement in the study, implementation factors and potential considerations of sustainability of model delivery service. Individuals who supported set-up and implementation of the study or are responsible for or have sound knowledge of important considerations will be eligible to take part.

Additionally, we will invite OH and wellbeing leaders from diverse sectors to participate in an interactive knowledge mobilisation day. Study findings will be shared and round table discussions held to explore opportunities and obstacles in delivering HWS through the supply chains in other industry sectors.

9.2.3 Participant recruitment

All champions in intervention SMEs will be invited to take part in focus groups. A purposive sampling method will be used to identify and invite individuals to take part in the stakeholder interviews. The purposive sampling will be a collective effort by the research team, champions at each of the intervention SMEs, and leaders in each SME and LEO to identify those who would be knowledgeable about the topic of the interview and likely to take part. We will then send a participant information sheet to those people who we purposively identify and will be able to answer any questions they may have and consent them into the study if they are willing to participate..

9.2.4 Study Procedures:

Organisations' preference for offering face-to-face, telephone or video conferencing options will be accommodated. Interviews and focus groups will be recorded and transcribed to aid analyses.

9.2.5 DATA

Qualitative data to be collected (Champions and stakeholder level data)

We'll record contact between champions and advisors, and will conduct focus groups with the former to explore their training experience, resulting acquisition and maintenance of skills over the study period, and confidence in delivering the study intervention. Questions will further examine sustainability of skills acquired and level of supplementary training required to achieve established competency goals and maintain skill proficiency.

See the Interview topic guide appendix for an example topic guide that will be used to interview participants. Broadly, the qualitative work will explore champions and advisors training experience, resulting acquisition and maintenance of skills over the study period, and confidence in delivering the study intervention. Questions will further examine sustainability of skills acquired and level of supplementary training required to achieve established competency goals and maintain skill proficiency. The topic guide will be further developed to take account of earlier work packages and then iteratively modified as data generation and analysis progresses.

We anticipate interview (1-2-1 and focus group) sessions will be held online (with in-person sessions available if required). Interviews will be recorded using Microsoft Teams with back-up encrypted Dictaphone device; audio data will be transcribed verbatim. Transcription will be conducted by Microsoft Teams or by an external contracted provider i.e. audio files created on an encrypted Dictaphone will be sent via upload to a cloud-based depository portal and processed by Accuro, an external transcription service approved by the Guy's and St Thomas NHS Foundation Trust. Recordings will be immediately deleted after the transcription has been completed.

Data handling and record keeping

The study team will not disclose or use for any purpose other than performance of the study, any data, record, or other unpublished confidential information disclosed to those individuals for the purpose of the study. Prior written agreement from the Host or its designee will be obtained for the disclosure of any said confidential information to other parties.

Digital recordings of interviews will be made using a Dictaphone device (for telephone and in-person interviews) and Microsoft Teams (for online interviews) and transcribed using Microsoft Teams or through Accuro, an external transcription service approved by the Guy's and St Thomas NHS Foundation Trust. Files will be downloaded and securely stored at Affinity Health at Work only on a password protected shared drive, with limited access by the authorised study staff only. Recordings and transcriptions made on Teams will be immediately deleted from the Microsoft Cloud once they have been securely downloaded. The saved transcripts will be pseudonymised and identified by unique participant IDs and a member of the Affinity research team will check the transcript for clarity and accuracy. The recorded interview will then be deleted soon after transcription has been checked.

Data storage procedures will follow Affinity Health at Work standard operating procedures for research.

All the information/data collected for this study from participants will be securely stored in folders on the Affinity Health at Work secure servers, folders will be password protected and can only be accessed by the research team. The recording equipment used to record the

interviews will be erased after each interview has been uploaded to the secure folder on the Affinity Health at Work server.

The pseudonymised interview recording, pseudonymised transcripts, and the consent form with identifiable personal information, will be stored in separate locked and protected folders on Affinity Health at Work secure servers in line with GDPR requirements for the duration of the study. Each file will have the unique study ID for each participant, and it will only be possible to identify the participant by looking at the consent form and linking this study ID to the other documents. Data will remain pseudonymised to allow participants to withdraw their data from the study, should they desire. The protocol for withdrawing data will be explained to participants in the PIS.

All qualitative data collected will not be stored with any identifying information. A code number will be allocated to each qualitative participant and will be stored securely, to ensure that participants cannot be identified from your response.

Affinity Health at Work will be the data processor for this qualitative study, working on behalf of Guy's and St Thomas' NHS Foundation Trust as the data controller, and is responsible for looking after the information and using it properly.

Data will only be held where there is a legitimate need to do so. Once the stage of the study which involves inviting participants to take part in research and asking for their express consent is complete the contact details will be securely destroyed.

All data will be retained for two years after the end of the research study as per GSTT guidance before being destroyed (deleted electronically).

A full description of the data flow is provided in the study's Data Protection Impact Assessment document.

Data Sharing

The data generated by this work package will be created and stored at Affinity Health at Work, as they are operating as a Data Processor on behalf of GSTT. The only components of this work package that will be stored within GSTT will be the finalised analysis report of the qualitative interview data. The completed consent forms will be transferred from Affinity Health at Work to GSTT for the purposes of archiving, and the analysis report will contain only anonymized data about the participants who completed interviews. Other outputs from the qualitative interview analysis other than the analysis report (i.e. annotated transcripts, etc) will be retained at Affinity Health at Work.

Audio files created on an encrypted Dictaphone will be sent via upload to a cloud-based depository portal and processed by Accuro, an external transcription service approved by the Guy's and St Thomas NHS Foundation Trust.

At the end of the study and with consent from participants, the final anonymised dataset will be uploaded to OSF (a publicly accessible) data repository for future ethnically approved research. This has been highlighted on the PIS and the ICF, and participants will have the option to with-hold their anonymised data if they desire.

9.3 Analysis (WP2-4):

Quantitative data and economic analysis Participant questionnaire

Questionnaire responses will be converted into relevant outcome metrics (e.g. work engagement score, health economic utility scores). Employee-level outcome data collected at baseline, 6 months, 12 month and 18 months will be analysed using two-level multilevel regression models, with employee participants nested within SMEs. Analyses will include an interaction term between the intervention group and time period, to assess differences in change in work engagement (and then separately for each of the secondary outcome measures) between baseline, 6-months (work engagement only) and 12 months (i.e. short-term intervention effect), and between baseline and 18 months (long-term intervention effect) between the intervention and the control SMEs.

Further analyses will assess effect modification by organisational (information collected at the recruitment process like workforce size, sector, relative size of customer, and length of business operation) and intervention delivery factors (dependent on the variation in the recruited SMEs), including a multiplicative interaction between intervention group and each of the factor under consideration. If there is evidence of significant effect modification, we will stratify our analyses accordingly to determine the strength and the direction of the effect by levels of the modification factor.

Economic evaluation will take the form of a cost-consequence analysis (whereby disaggregated non-monetised changes in outcomes are presented alongside costs to inform decision making) and a Social Return on Investment (SROI) [24,25], whereby benefits observed after 12 and 18 months are monetised using published sources, and potential longer-term impacts are explored using different assumptions about the sustainability of changes in behaviour and health. Resources used in intervention delivery will be assessed using data collected in WP2 and costed using a micro-costing approach [26]. Resources used by companies and employees will be assessed using questionnaire data (example measures listed above in WP1), and costs incurred will be calculated using relevant unit cost data. Differences in the results will also be presented in terms of the person- and SME-level moderators defined above and the perspective of the analysis, which will include the employer, employee and wider economy perspectives.

Engagement activity log

Information recorded in the activity log will be used to inform the process evaluation (WP4). Specifically, analysis will include:

- i) Collation of the HWS implemented in the SMEs. The activities offered (as identified in the activity log and triangulated by LEO service use), can then be compared with data on uptake and evaluation (as identified in the follow-up employee survey) within each SME organisation.
- ii) Review of the communications cascaded. This data will be collated and cross-referenced to explore variations in the volume or nature of communications within each SME.

iii) Thematic analysis of reflections on obstacles and opportunities as recorded by the H&W champions and advisor throughout the study duration. This data will provide valuable information on how the HWS were implemented within the SME organisations, and how the SMEs worked with their LEO throughout the implementation contributing to the process evaluation. Learnings from the implementation of this 'activity log' process will be captured by the research team and shared through our project reporting and dissemination activities.

Qualitative data

Data will be analysed using inductive and deductive thematic analysis. We will draw on the Implementation Outcome Framework [28] as applied by Yarker and colleagues in a recent meta-synthesis of the barriers and facilitators to workplace mental health interventions to inform our approach [29].

OH and wellbeing leaders from diverse sectors will be invited to the interactive knowledge mobilisation day. For this dissemination event, we will invite a wide range of important parties through our existing professional networks. These will include the wider research team, as well as our stakeholders, including NIHR/DHSC staff, those leading HWS in the participating SMEs and LEOs (OH, Human Resources and Wellbeing reps), their Financial Directors and the Head of Procurement from the LEOs. We will also invite members of the EPSG, wider colleagues working in the area of work and health research, and representatives from other LEOs across diverse sectors, with whom we will explore the possibility of implementing this model in their companies and their supply chain. Study findings will be shared and round table discussions held to explore opportunities and obstacles in delivering HWS through the supply chains in other industry sectors.

9.3.1 Outputs:

- i) Study experience of champions and views of the acquired skills during the study period and beyond
- ii) A list of perceived benefits and obstacles of implementation of HWS intervention for LEOs and SMEs
- iii) Production of a detailed logic model to inform research and practice
- iv) A list of organisations willing to explore a supply chain approach to HWS delivery and sector-specific considerations to inform policy decisions

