6 STUDY DESIGN & FLOWCHART

6.1 Study Design

A prospective matched control cluster study design involving nine intervention and nine matched control SMEs from the supply chain of three participating LEOs (JLR, Hampshire and Isle of Wight Health Integrated Care Trust and Transport for London) across diverse sectors. Collaboratively, we will tailor a multi-component HWS intervention to each SME's needs. Delivered by the LEO, it will likely include raising awareness about workplace health and wellbeing, health promotion, preventing mental ill health, and training managers in health and wellbeing (H&W) conversations. H&W champions will be recruited from each intervention SME to facilitate delivery and, supported by a qualified health and work advisor to develop effective communications to alert SME employees of available services and organise relevant activities. Effectiveness (work engagement) will be evaluated before the roll-out of the intervention (baseline), during the intervention (6-months), at the end of the intervention period (12-months) and 6 months later (18-months). An economic evaluation of the intervention will use cost-consequence and SORI frameworks. A process evaluation will identify implementation obstacles and facilitators, complemented by a discrete choice experiment (DCE) involving large numbers of SME decision makers from diverse sectors to ascertain the value they place on HWS and their willingness-to-pay for a range of potential HWS interventions.

To address the research aims and objectives, the study comprises three phases with five iterative work packages (WPs) addressing the study's research aims and objectives.

- Phase 1: Preparation and service evaluation activities
 - WP1: Preparatory work to set up the delivery and evaluation of intervention.
- Phase 2: Implementation (Participating x3 LEOs and x18-24 SMEs)
 - WP2: Study implementation with a running time of 18 months in each SME (including 12 months of intervention period and follow-up 6 months later).
- Phase 3: Evaluation
 - WP3: Intervention effectiveness evaluation; economic evaluation.
 - WP4: Process evaluation

- WP5: Discrete Choice Experiment (DCE) to examine the willingness of SMEs to pay for activities.

A detailed description of the planned methodologies is outlined in the following WPs.

7 Phase 1: Preparation and service evaluation activities

7.1 Work Package 1: Intervention co-design and preparation for the HWS intervention (Lead: JY/AS)

7.1.1 Objectives:

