8.1.5 STUDY FLOW DIAGRAM (INTERVENTION and CONTROL ARM)

8.1.6 Participant Selection

Participants recruited into the study will be drawn from the 18-24 SMEs recruited to take part in the study and we will work with the local collaborator at each SME to develop an acceptable method to invite participants to take part. We will monitor recruitment from each participating centre and will relay information back to the local sites, so they are aware of the recruitment uptake.

Sample size calculation and justification

A previous study of a workplace intervention to build and sustain work engagement [27] suggests a mean (SD) work engagement score of 5.08 (1.40) in the control and 5.76 (0.86) in the intervention group. As the proposed intervention is SME-based, sample size calculations must account for clustering effects. With the rho of 0.1 and the above values for expected change in work engagement scores, seven SMEs per intervention arm ensure 90% power at a 5% significance level (2-sided) to detect differences in the primary outcome. To account for participant attrition, we plan to over-sample with nine to twelve SMEs per arm, depending on the availability of interested SMEs, and to maximise the recruited employee sample per SME.

Given the workforce size of SMEs (between 10 and 249 employees), and assuming a uniform response rate across the recruited SMEs no greater than 50%, the anticipated number of participating employees per SME will range from 5 to 125, equivalent to an average of 65 employees per SME. Put together, the anticipated sample size across the minimum of 18 recruited SMEs would be 1170 employees, rising to 1560 employees if we can recruit the full complement of 24 SMEs. This ensures robustness in detecting meaningful changes in work engagement attributable to the proposed intervention.

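### No primary time point is fixed for work engagement, although the sample size powers a single 5% comparison

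*Protocol*

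**What the plan says.** Protocol section 9.1.2 lists work engagement (UWES) as the primary outcome without a time point. Section 6.1 says effectiveness on it is evaluated before roll-out and then "during the intervention (6-months), at the end of the intervention period (12-months) and 6 months later (18-months").

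Section 9.3 fits a two-level model with a group-by-time interaction and uses it to compare the arms on change from baseline to "6-months (work engagement only) and 12 months (i.e. short-term intervention effect), and between baseline and 18 months (long-term intervention effect"). The short-term label covers two times and the long-term label one. None is called primary, no order is given, and nothing says whether the interaction is tested as a whole or contrast by contrast.

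The sample size paragraph in section 8.1.6 takes "a mean (SD) work engagement score of 5.08 (1.40) in the control and 5.76 (0.86) in the intervention group" from an earlier workplace study and states that "seven SMEs per intervention arm ensure 90% power at a 5% significance level (2-sided") to detect a difference in the primary outcome. No follow-up time is attached. Section 14 only refers back to the work packages.

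**The concern.** The time of assessment is part of the definition of a primary outcome, and it identifies the hypothesis to which the significance level and power apply. Here one level and one power figure stand against two or three results of equal rank. If the arms differ at 12 months but not at 18, or the reverse, the protocol does not say whether the intervention was effective. It also leaves open whether more than one chance of a positive result is being taken at 5%. The trial's stated aim is to assess effectiveness on work engagement, and section 20 expects the findings to inform government policy, so the main conclusion should not depend on a choice made after the results are seen.

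**Working it through.** **Inputs from section 8.1.6.** Means and SDs 5.08 (1.40) and 5.76 (0.86); intracluster correlation ρ = 0.1; average m = 65 employees per SME; two-sided 5%; 90% power; 9 to 12 SMEs planned per arm.

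**Assumption.** The documents give no correlation r between the test statistics at different times. I use 0.5-0.8 as plausible and show other values.

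**1. The plan's own figure.** SMEs per arm by the normal approximation with a design effect:

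k = (SD₁² + SD₂²)/δ² × [1 + (m − 1)ρ]/m × (z₁₋α/₂ + z₀.₉₀)²

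- SD₁² + SD₂² = 1.9600 + 0.7396 = 2.6996
- δ² = 0.68² = 0.4624; ratio 5.838
- [1 + 64 × 0.1]/65 = 7.4/65 = 0.1138; product 0.6647
- (1.960 + 1.282)² = 10.507
- k = 0.6647 × 10.507 = **6.98, so 7 per arm** (power 90.1%)

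The stated 7 is reproduced. It is valid for a comparison at any single time, but it covers only one comparison.

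**2. False-positive chance if any significant contrast counts.** For independent tests it is 1 − 0.95² = 9.75% (two) and 1 − 0.95³ = 14.3% (three). For equally correlated two-sided z tests, each at 5%, it is P(any |Z| > 1.96):

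| Correlation r | Two contrasts (12, 18 months) | Three contrasts (6, 12, 18 months) |
|---|---|---|
| 0.3 | 9.5% | 13.6% |
| 0.5 | 9.1% | 12.5% |
| 0.7 | 8.4% | 10.9% |
| 0.8 | 7.8% | 9.8% |
| 0.9 | 7.0% | 8.4% |

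Two checks agree. Change-from-baseline contrasts built from autoregressive correlations of 0.5-0.8 give 11.2-11.7% for three contrasts. Cluster-level t tests with 9 or 12 SMEs per arm, at r = 0.5-0.8, give 9.9-12.8% for three and 7.8-9.4% for two.

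**3. Cost of making several times co-primary.** Same formula, Bonferroni split, 90% power per contrast:

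- Two contrasts, α = 0.025: (2.241 + 1.282)² = 12.411; k = 0.6647 × 12.411 = 8.25, so 9 per arm.
- Three contrasts, α = 0.05/3: (2.394 + 1.282)² = 13.510; k = 0.6647 × 13.510 = 8.98, so 9 per arm. With 7 per arm, power per contrast would be 80.3%.

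Nine is the planned minimum. Section 8.1.6 presents the step from seven to nine or more as the allowance for attrition, so at nine per arm that reserve would be gone.

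**The case against.** A reader might infer that the false-positive rate of this trial is about double the stated 5%. The protocol does not support that as a plain statement, for four reasons.

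- It contains no rule that any significant contrast establishes effectiveness. Section 9.3 specifies an interaction term and does not say how it is tested; one joint test would hold 5%.
- Three equal tests is the least favourable count. Section 9.3 names two effects. Section 9.1.2 describes the 6-month contact as a short mid-intervention survey, and the economic analysis monetises benefits only at 12 and 18 months. With two contrasts the figure is about 8-9%.
- The correlation is assumed.
- A multiplicity rule may sit in a statistical analysis plan that is not shown, so its absence here is no finding.

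A reader might also infer that the power statement is void. It is not: it reproduces exactly and lacks only a time label.

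All of this stands, and it limits what can be said about error rates. It does not supply the missing time point. Twelve months may look like the natural choice, but no section says so, and 18 months has its own named effect. A joint test, if intended, would not be the single mean difference that 8.1.6 powers.

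**Conclusion.** The protocol does not fix a primary time point for its sole primary outcome, so its single 5% level and 90% power are not tied to any one of the contrasts in section 9.3. This is a gap in the definition of the primary outcome, not merely analysis detail left for later. The error-rate consequence is conditional. If significance at any time would count, and correlations are 0.5-0.8, the chance of a false claim is about 8-9% for two contrasts and about 10-13% for three; under a joint test it is 5%. The sample size of seven SMEs per arm is correct, by the plan's apparent method, for one time point.

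**What to change.** State in 8.1.6 and 9.3 one primary contrast to which the two-sided 5% level and 90% power apply. An example is the between-arm difference in change in work engagement from baseline to 12 months, the end of the intervention, with the 6- and 18-month contrasts secondary. This takes a sentence or two and leaves seven SMEs per arm unchanged. The downside is that the secondary time points can no longer carry the primary claim.

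The choice of time is the authors' to make. If they want 12 and 18 months, or all three times, to be co-primary, they should state a joint test or an alpha split and restate the number of SMEs. A Bonferroni split over three contrasts needs 9 per arm by the plan's own formula, which leaves no attrition reserve at the lower end of planned recruitment.
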